7.5.1.1 Sensitivity Analyses

To assess the robustness of the primary efficacy analysis, additional sensitivity analyses will be carried out using the following approaches:

- Following the same procedure as the primary analysis, considering the All Evaluable Subjects population in place of the All Randomized Subjects population.
- A worst-case analysis that will repeat the primary analysis on the ITT population where any missing information that is consequential to the evaluation of the primary endpoint will be considered as an event.

7.5.1.2 Subgroup Analyses

All analyses described in this section will be performed on the ITT Population. Table 7.5.1.2-1 below shows the subgroups of interest for analyses of efficacy data. If the value of the grouping variable cannot be determined for a subject, the subject will be excluded from the corresponding subgroup analysis.

Table 7.5.1.2-1: Subgroups of Interest for Efficacy Assessments

Grouping Variable	Subgroups
Event at entry	Acute ischemic stroke Transient ischemic attack
Time since onset of symptoms detected to randomization	< 24 hours 24 - 48 hours
Lacunar infarct at entry	Yes No
Oxfordshire Community Stroke Project (OCSP) Subtype (only for stroke) at entry	Total Anterior Circulation Stroke (TAC) Lacunar Stroke (LAC) Partial Anterior Circulation Stroke (PAC) Posterior Circulation Stroke (POC)
ABCD2 ^a Score (only for TIA) at entry	4-5 (moderate)

Table 7.5.1.2-1: Subgroups of Interest for Efficacy Assessments

Grouping Variable	Subgroups
	6-7 (high)
Age	< 65 years old ≥ 65 to < 75 years old ≥ 75 years old
Gender	Male Female
Race	White Black or African American Asian Other
Geographic Region	North America Europe Asia / Pacific

^a age, blood pressure, clinical features, duration, diabetes

7.5.2 Secondary Efficacy Analyses

The same approach used in the primary analysis will be repeated on the secondary endpoints.

- The incidence of major adverse cardiovascular events (MACE) by Day 90, defined as a composite of adjudicated recurrent stroke, myocardial infarction, or CV death
- The incidence of a composite of adjudicated recurrent ischemic stroke, myocardial infarction, or CV death by Day 90
- The incidence of adjudicated symptomatic recurrent stroke (including fatal and non-fatal) by Day 28
- The incidence of the composite of unrecognized brain infarction assessed by MRI at Day 28 and MACE by Day 90

In addition, a sequential testing procedure will be used for the primary and MACE endpoints as described below.

- 1) If a dose-response relationship is established for the primary endpoint at the one-sided 0.15 level, then the primary analysis will be repeated at a one-sided alpha level of 0.025.
- 2) If this analysis at the one-sided 0.025 level also demonstrates a dose-response relationship, then the dose-response relationship for the MACE endpoint will be tested using a one-sided alpha level of 0.025.

Each of these sequential testing analyses will be performed. Their interpretation will be guided by the sequential testing procedure.

7.5.3 *Other Efficacy Analyses*

The primary analysis will be repeated for the composite endpoint of recurrent ischemic stroke or any adjudicated arterial thrombotic events up to 90 days. As well, the primary analysis will be repeated using each of its components, individually, as the response variable.

Additionally, the following exploratory analyses may be explored:

- [REDACTED]

7.6 *Safety Analyses*

Analysis of all safety data will be conducted on all treated subjects and will follow the BMS guideline of analysis of safety data⁹. Safety will be summarized for each parameter by treatment group, as well as for all subjects receiving BMS-986141. Summaries of the frequency of subjects experiencing certain events, such as adverse events, elevated labs or vital signs, or elevated ECGs, will be summarized by treatment and study time period (1A, 2A, 2B), and for study part 2.

The evaluation of safety is based on adjudicated bleeding events, clinical adverse events (AEs), vital signs, ECG results, and clinical laboratory results.

All AEs will be coded and grouped into Preferred Terms (PT) by System Organ Class (SOC), using the most current available version of Medical Dictionary for Regulatory Activities (MedDRA). Summaries of AEs will use the version of MedDRA that is current at the time of database lock. All recorded adverse events will be listed and tabulated by SOC, PT, treatment and overall. Values for ECGs, vital signs, and clinical laboratory test results will be summarized by treatment. Abnormal results for ECG, vital signs and clinical laboratory tests that fall outside the pre-specified criteria will also be listed and summarized. In addition, ECG readings will be evaluated by the Investigator and abnormalities, if present, will be listed.

7.6.1 *Major Bleeding and Clinically Relevant Non-Major Bleeding*

The proportion of subjects with adjudicated bleeding events which occur on or after the first dose of study treatment and within 4 days after the last dose of study treatment will be summarized by treatment. Point estimates and 95% exact CIs for event rates of each of the below bleeding endpoints will be presented by treatment, together with point estimates and 95% exact CIs for the difference of event rates between each BMS-986141 arm and placebo. The following bleeding endpoints will be analyzed using these methods.

- The proportion of subjects with the composite of adjudicated major bleeding and CRNM bleeding
- The proportion of subjects with all reported bleeding
- The proportion of subjects with intracranial hemorrhage

All adjudicated bleeding events will be listed. In addition, the proportion of subjects with confirmed major bleeding or clinically relevant non-major bleeding events occurring during the treatment period will be summarized by treatment group for each of the following factors.

- Stroke severity (based on National Institutes of Health Stroke Scale NIHSS) at study entry
 - NIHSS Score of 0 (No stroke symptoms)
 - NIHSS Score of 1-4 (Minor stroke)
 - NIHSS Score of 5-15 (Moderate stroke)
- Lacunar infarct at study entry
 - Yes
 - No

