For each candidate model ($m=1, 2$), the contrast test statistic (z_m) is calculated as standardized linear combinations of the estimated event rate on the logit scale from the logistic regression using the optimal contrast coefficients associated with that candidate model.

A multiplicity-adjusted critical value will be determined from the joint multivariate normal distribution of the contrast test statistics at the overall one-sided alpha level of 0.15. If either test statistic that exceeds this critical value, a dose-response relationship will be demonstrated.

Modelling and Estimation

The model for estimation will be selected from among the two candidate models with a contrast test statistic that is greater than or equal to the multiplicity-adjusted critical value. If both

candidate models have such contrast test statistics, then both models will be employed using a weighted averaging technique based on their relative Bayesian Information Criteria (BIC), for the purposes of estimation. If neither candidate model has a contrast test statistic that is greater than or equal to the multiplicity-adjusted critical value, then the analysis will end, indicating that a dose-response relationship cannot be established.

In this manner, the point estimates for the means will be generated from the selected model as described in the efficacy analyses in [Section 7.5](#).

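### Outside the primary and MACE, the efficacy endpoints inherit the one-sided 0.15 decision rule with no gate and no multiplicity control

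*SAP*

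**What the plan says.** SAP 7.1.2 sets out the gMCP-Mod method used for efficacy. Its critical value is fixed "at the overall one-sided alpha level of 0.15", adjusted for the two candidate models within one endpoint. The decision rule follows: "If either test statistic that exceeds this critical value, a dose-response relationship will be demonstrated". The same critical value decides which model is fitted. If neither contrast reaches it, the analysis stops there.

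SAP 7.5.2 then extends the method: "The same approach used in the primary analysis will be repeated on the secondary endpoints". Four endpoints are listed, MACE first. A sequence for the primary and MACE is added on top. If the primary passes at 0.15, "then the primary analysis will be repeated at a one-sided alpha level of 0.025". If that also succeeds, "then the dose-response relationship for the MACE endpoint will be tested using a one-sided alpha level of 0.025". On these sequential analyses the SAP adds: "Their interpretation will be guided by the sequential testing procedure".

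SAP 7.5.3 repeats the primary analysis on a composite of recurrent ischemic stroke and arterial thrombotic events to Day 90. For the primary composite, "the primary analysis will be repeated using each of its components, individually, as the response variable".

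Protocol 8.4.2.2 gives the same sequence. For the remaining secondary endpoints it refers only to similar methods and states no level.

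**The concern.** The 0.15 level is a signal-finding level, and Protocol 8.1 and SAP 5 use it to power the single primary test. Carried to other endpoints with its decision wording intact, it lets a clinical endpoint be reported as showing a dose-response on weak evidence. Nothing makes that conditional on the primary, nothing adjusts across endpoints, and neither document calls these analyses descriptive.

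At stake is what the report may conclude if the primary fails. Several overlapping endpoints would remain, each with a 15% chance of a false positive and each covered by a rule that says the relationship has been demonstrated.

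**Working it through.** **1. Which level applies where**

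| Endpoint | Level stated | Gate |
|---|---|---|
| Primary | one-sided 0.15, then 0.025 | start of the sequence |
| MACE by Day 90 | 0.025 in the sequence; also listed under the repeated primary approach | primary at 0.025 |
| Other three secondary endpoints | none beyond the repeated approach (0.15) | none |
| SAP 7.5.3 endpoints | none beyond the repeated primary analysis (0.15) | none |

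**2. Reproducing the plan's own figure**

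- Inputs (SAP 5 and 7.1.2, Protocol synopsis): placebo rate 14%; 30% maximum relative reduction; 75% and 90% of that maximum at the lower doses; so rates of 14%, 10.85%, 10.22% and 9.8%. Allocation is 348/347/347/270, with 1240 evaluable, and the dose scale is 0, 1, 2, 2.3.
- Candidate shapes: Emax d/(1+d); logistic 1/(1+exp((1−d)/0.1)).
- With optimal contrasts on the logit scale, the two statistics correlate at 0.97.
- Power at one-sided 0.15 is 78.1% with 1240 subjects and 79.6% with 1312. The plan says at least 80%, from 1000 simulations with standard error √(0.8×0.2/1000) = 1.3 points. That is close enough to confirm the set-up.

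**3. Critical values**

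Solving 1 − Φ₂(q, q; 0.97) = α gives q ≈ 1.13 for α = 0.15 and q ≈ 2.05 for α = 0.025. A MACE statistic between these values leads to a fitted model under the repeated primary approach, but fails the gated test.

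**4. Limits that need no event rates**

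Take all nulls as true, each endpoint at 0.15, and non-negative correlation between statistics:

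- Perfect correlation: 15%.
- Four independent endpoints: 1 − 0.85⁴ = 47.8%.
- Three independent endpoints: 1 − 0.85³ = 38.6%.

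**5. Overlapping endpoints**

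The documents give no secondary event rates or correlations, so these are assumed. Events were drawn independently with the same rates in every arm. Endpoints were built from shared components, and both contrasts were applied to each with a pooled variance. There were 8000 trials per case. Hemorrhagic stroke was set at a few tenths of a percent throughout.

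| Assumed: ischemic stroke to Day 28 / later / MI or CV death / MRI infarct | Any of four | Any of three non-MACE | Any of four or primary | Primary alone |
|---|---|---|---|---|
| 4% / 1.5% / 1% / 10% | 28.5% | 27.8% | 31.5% | 15.5% |
| 2% / 1% / 0.7% / 12% | 31.1% | 30.2% | 33.6% | 15.2% |
| 6% / 3% / 2% / 8% | 27.4% | 26.5% | 30.6% | 14.7% |
| 3% / 3% / 2% / 11% | 30.8% | 29.9% | 34.8% | 15.5% |

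Subtracting the last column from the one before it gives the chance that a secondary endpoint is declared while the primary fails: 31.5 − 15.5 = 16.0%, 33.6 − 15.2 = 18.4%, 30.6 − 14.7 = 15.9% and 34.8 − 15.5 = 19.3%.

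**6. Comparison**

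Testing all four at one-sided 0.025 without a gate gives 6% to 7%. MACE under the SAP's gate gives 0.2% to 0.4% in these simulations, and at most 2.5% by design.

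The SAP 7.5.3 endpoints are left out of these figures. Counting them could only raise the chance of at least one false positive.

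**The case against.** **The level is inferred.** The 7.5.2 sentence repeats an approach and mentions no alpha. The SAP treats the level as separable, since it reruns the primary analysis at 0.025. The protocol likens the other secondary endpoints to both the primary and MACE, which have different levels. This stands to a degree: 0.15 is not written beside these endpoints. But no other level is written anywhere, and the SAP's general efficacy method contains only 0.15. On the milder reading the level is simply unstated, and the same sentence is needed.

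**Unadjusted secondary analyses are ordinary in Phase 2.** True, and the plan nowhere says that results outside the sequence will support efficacy claims. The problem is narrower. The plan attaches a conclusion to a 0.15 threshold and does not mark these analyses as exploratory.

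**Stronger readings that the documents do not support.**

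- A reader might infer that MACE has two conflicting success rules. The SAP says the sequence guides interpretation, and Protocol 8.4.2.2 gives MACE only the gated 0.025 level. The sequence is not undone.
- A reader might take a figure near 28% as a property of the design. It depends on event rates that the documents do not supply.
- A reader might conclude that the stopping rule for model fitting should go for these endpoints. That is a separate method change, and the error-rate argument does not support it. SAP 7.5.1 already presents raw proportions and relative risk reductions with confidence intervals.

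**Conclusion.** The concern holds for the three non-MACE secondary endpoints and those in SAP 7.5.3. Followed as written, the plan permits ungated declarations at one-sided 0.15, including after a failed primary.

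Under the global null, with each endpoint read at 0.15, the chance of at least one false secondary dose-response is about 27% to 31% under the assumed rates, within limits of 15% to 48%. The three non-MACE endpoints alone give about 27% to 30%, so the result does not turn on how MACE is read. A secondary endpoint is declared while the primary fails in about 16% to 19% of such trials.

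For MACE, only an ambiguity remains. The claim is governed by the gated 0.025 test, but it is unclear whether 1.13 or 2.05 decides its model selection and fitted estimates.

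**What to change.** In SAP 7.5.2 and 7.5.3, with Protocol 8.4.2.2 aligned, state that:

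- the one-sided 0.15 decision level applies to the primary endpoint only;
- the gated one-sided 0.025 test is the only decision rule for MACE, and name the critical value used for its model selection;
- all other secondary endpoints and the 7.5.3 endpoints are reported with nominal p-values and estimates, without any conclusion that a dose-response has been demonstrated.

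The rule on when a model is fitted can stay. If it is kept at 0.15 for these endpoints, say that it is a fitting rule and not a finding.

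This needs no extra subjects, data or design change. It does need a small protocol clarification as well as SAP wording, and it leaves fewer nominally positive secondary statements.

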1.4.1 Clinical Pharmacology and Safety

Preliminary data have been reviewed on a total of 116 subjects who have received single doses of BMS-986141 of up to 150 mg and multiple doses of up to 30 mg QD for up to 14 days in study CV006003. This includes subjects receiving multiple doses of 20 mg QD or placebo co-administered with ASA 325 mg QD for up to 14 days and subjects who received single doses of BMS-986141 in the presence of itraconazole, a strong cytochrome P450 (CYP) 3A4 inhibitor. Preliminary results show dose proportional PK and a consistent concentration-dependent PD effect. In addition, exposures in subjects who also received itraconazole increased up to 8-fold and the half-life of BMS-986141 increased ~3-fold.

Review of preliminary safety data showed no clinically significant AEs or laboratory abnormalities, including coagulation profiles, template bleeding times, BUN, creatinine, bilirubin, or hepatic enzymes. This includes all subjects who received BMS-986141 co-administered with ASA and BMS-986141 co-administered with itraconazole.

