1.4.1.1 Pharmacokinetics of BMS-986141

BMS-986141 was rapidly absorbed following oral administration to fasted healthy subjects, with maximum concentrations achieved between 1.75-3 hours. The mean terminal half-life of BMS-986141 was between 35.2-45.5 hours. The accumulation index was < 2 (ranging from 1.3 to 1.9). Both maximum concentration (C_{max}) and total drug exposures of BMS-986141 increased in a dose-proportional manner.

There are 3 major circulating metabolites of BMS-986141; BMT-162856 (700 – fold less active), BMT-181551, and BMT-162853. Exposures of BMT-162856 were 6.8-36.4-fold higher than BMS-986141, with the exposures of the other metabolites much lower than BMS-986141. The exposures of BMS-986141 and its major circulating metabolites are expected to be below no-observed-adverse-effect level (NOAEL) exposures at all doses. All metabolites are expected to have minimal contribution to the overall PD effect.

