A study visit will be performed on the day of hospital discharge. Subjects will be instructed to report any adverse events occurring after hospital discharge, including any occurrence of bleeding or signs or symptoms of recurrent stroke.

The study site will contact the subject by telephone on Day 10 \pm 3 days to assess study medication compliance and assess the subject's health status.

A study visit will be performed 28 \pm 3 days after the first dose of study medication. Head MRI will be performed for assessment of unrecognized brain infarctions. For subjects enrolled in Part 1 of the study, Day 28 will be the end of the treatment period and it is preferred that the study visit be performed on Day 28 or earlier.

Part 2 of the study will only be initiated after regulatory review of 90-day preclinical toxicology study reports and the updated Investigator Brochure. For subjects enrolled in Part 2 of the study, the treatment period will be 90 days. There will be no change in study visits through Day 28. Additional treatment period study visits for these subjects will occur 56 and 90 days after the beginning of the treatment period.

Pharmacokinetic (PK) sampling will be performed in all subjects. See [Section 5.5](#).

A sub-study conducted at select sites will enroll approximately 50 subjects per arm for which additional blood will be collected for analysis of platelet aggregation as a pharmacodynamic biomarker. See [Section 5.6](#).

Follow-Up Period

The follow-up period will last until the later of 90 days after the first dose of study drug or 30 days after treatment discontinuation. Subjects will be instructed to report any adverse events that occur during the follow-up period. No additional study assessments are planned at the follow-up visit, which may be an in-person study visit or if necessary conducted by telephone.

Duration of Study

The expected duration of the study, from first subject, first visit through the last subject, last follow-up visit (eg, the End of the study), is approximately 28 months.

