5 SAMPLE SIZE AND POWER

The primary efficacy endpoint of the study is the incidence of a composite of symptomatic ischemic stroke by Day 28 and unrecognized brain infarction at Day 28. Sample size calculations were performed for detecting a dose-response effect with the MCP-MOD methodology using simulations with the DoseFinding package in R⁴. Simulations of 1000 clinical trials were performed, assuming a true incidence for placebo of 14%, a maximum relative risk reduction of 30% for BMS-986141 8 mg relative to placebo, and relative reductions of 75% and 90% of the maximum for the 0.8 and 4.8 mg doses, respectively. Candidate models included an Emax model and a logistic model.

Initially, randomization will be limited to the two lower doses of BMS-986141 (0.8 mg or 4.8 mg) or placebo in a 1:1:1 ratio until after the DMC review of safety and laboratory data from the Day 28 study visit for at least 10% of planned total subjects (approximately 132 subjects). If the DMC recommends proceeding to inclusion of the highest dose (8 mg), subsequent randomization will be in a 1:1:1:1 ratio. Based on the staggered randomization as shown in in the table below and the assumptions above, the study will have at least 80% power to demonstrate a dose-response relationship, using a 1-sided type I error rate of 15%. A total sample size of 1312 randomized subjects accounts for about 5% of subjects without post-randomization data.

Table 5-1: Randomization Targets

	Placebo	0.8 mg	4.8 mg	8 mg
Prior to interim safety review by the DMC: 132 subjects (1:1:1 randomization ratio)	44	44	44	0
Additional subjects randomized while interim safety reports are being generated and reviewed by the DMC (not included in the DMC safety interim analysis): 100	34	33	33	0

Table 5-1: Randomization Targets

	Placebo	0.8 mg	4.8 mg	8 mg
subjects (1:1:1 randomization ratio)				
After interim safety review by DMC: 1081 subjects	270	270	270	270
Total: 1312 subjects	348	347	347	270

Note: Numbers shown for each treatment group are estimates based on randomization ratio. Actual numbers could be slightly different based on randomization block size and rate of enrollment.

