7.6.4 Adverse Events

All AEs will be summarized by SOCs and PTs for each treatment group and also listed.

Adverse events which occur on or after the first dose of study treatment and within 4 days after the last dose of study treatment will be tabulated. Events will be assigned to the study treatment administered to the subject. The proportion of subjects having an adverse event will be calculated as the number of subjects experiencing the event, divided by the total number of subjects receiving study treatment.

A high-level summary will be presented by treatment group that counts subjects experiencing any of the following:

- At least one AE
- At least one related AE

- Deaths
- At least one SAE
- SAE leading to discontinuation of study drug
- AE leading to discontinuation of study drug

The above summary will also be presented by treatment and study time period (1A, 2A, 2B), and for study part 2.

All AE listings will indicate the unique subject identifier, age, gender, current treatment, the date of onset, the date of resolution, day of onset relative to the start of treatment, action taken, investigator's assessment of severity and relationship to study drug. Additional listings will be provided for adverse events leading to discontinuation, serious adverse events, adverse events leading to death, and adverse events without a recorded resolution. Summaries of adverse events will include adverse events, adverse events by intensity, adverse events leading to discontinuation, and adverse events by relationship.

All adverse events will be further summarized according to demographic factors for each of the categories given below:

- Age category I, in years (< 65, ≥ 65)
- Age category II, in years (< 65, ≥ 65- < 75, ≥ 75)
- Gender (male, female)
- Race (White, Black or African American, Asian, American Indian or Alaska Native, Native Hawaiian or Other pacific islander, Other)

Where a subject has multiple adverse events within the level of summarization in a single analysis period, the subject will only be counted once at that level of summarization in the adverse event frequency tables.

When a subject has the same adverse event, based on preferred terminology, reported multiple times in a single analysis period, the following criteria, in order of precedence, will be used to select the event to be included in summary tables:

- Relationship to study medication
- Intensity of event

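### The bleeding rates and adverse event tables stop 4 days after the last dose, short of five half-lives on either of the protocol's own figures; a longer window should be pre-specified beside the 4-day one

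*SAP*

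**What the plan says.** SAP 7.6.1 analyses the composite of adjudicated major and CRNM bleeding, all reported bleeding and intracranial hemorrhage. Each gets a rate, an exact 95% CI and a difference from placebo. Events count if they occur from the first dose and "within 4 days after the last dose of study treatment will be summarized by treatment". SAP 7.6.4 applies the same rule to adverse events, where those "within 4 days after the last dose of study treatment will be tabulated". The general text of SAP 7.6 also speaks of tabulating all recorded adverse events and gives no time limit.

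The endpoint definition (SAP 4.4, Protocol 8.3.4) is confined to the treatment period and mentions no days after dosing. The breakdowns by NIHSS and lacunar infarct in SAP 7.6.1 return to that wording, so one section uses two windows.

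On pharmacokinetics, Protocol 1.4.1.1 states "The mean terminal half-life of BMS-986141 was between 35.2-45.5 hours", gives an accumulation index of 1.3 to 1.9, and says that "total drug exposures of BMS-986141 increased in a dose-proportional manner". Protocol 3.3.1, in the contraception criteria, equates five half-lives with 6 days.

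On follow-up, Protocol 3.1 states: "The follow-up period will last until the later of 90 days after the first dose of study drug or 30 days after treatment discontinuation". Tables 5.1-2 and 5.1-3 schedule non-serious adverse events and concomitant medications at the follow-up visit.

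**The concern.** A post-dose window in a safety analysis is meant to capture events that occur while drug is still present. Four days is only two to three of the stated half-lives. Protocol 5.3.2 defines a CRNM bleed by the need for medical treatment or evaluation, or by discontinuation of study drug, so it need not be serious. Such a bleed on Day 5 or 6 after stopping would enter no rate, no confidence interval and no comparison with placebo. A late major bleed would likewise be absent from the adjudicated rate, although it would appear among the serious events.

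Bleeding is the main safety outcome, and the trial informs the choice of dose. Because exposure is proportional to dose, the absolute amount of drug left at the cut-off rises with dose, although the percentage left does not.

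**Working it through.** **Inputs.** Window: 96 h after last dose (SAP 7.6.1, 7.6.4). Terminal half-life T: 35.2 to 45.5 h. Accumulation index R: 1.3 to 1.9, with dose-proportional exposure (all Protocol 1.4.1.1). Five half-lives = 6 days (Protocol 3.3.1). Dosing every 24 h.

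**1. The protocol's own washout figure.** 5 × 35.2 / 24 = 7.3 days and 5 × 45.5 / 24 = 9.5 days. The stated 6 days is not reproduced: it needs T = 6 × 24 / 5 = 28.8 h, below the stated range. Four days is short of both figures.

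**2. Drug left at 96 h, three models.**

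- *Single-phase decay at the terminal half-life*, 2^(−96/T): 2^(−96/35.2) = 15.1% and 2^(−96/45.5) = 23.2%. With T = 28.8 h it is 9.9%. This model implies an accumulation index 1 / (1 − 2^(−24/T)) of 2.7 to 3.3, against the reported 1.3 to 1.9, so it is an upper figure.
- *Terminal half-life and accumulation index together*, as a share of average steady-state concentration: (1 − 1/R) × (24 ln 2 / T) × 2^(−72/T) / (1 − 2^(−24/T)). This assumes that R is AUC-based and that the terminal phase has begun by 24 h. R = 1.3, T = 35.2 gives 7.0%; R = 1.9, T = 45.5 gives 18.9%.
- *Effective half-life from R alone*, 24 ln 2 / [−ln(1 − 1/R)]: 11.3 to 22.3 h, leaving 0.3 to 5.0%. This sets the stated terminal half-life aside.

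**3. Amount left in the 8 mg arm.** Single-phase: 8 × 0.151 = 1.2 to 8 × 0.232 = 1.9 mg-equivalent. Joint fit: 8 × 0.070 = 0.6 to 8 × 0.189 = 1.5 mg-equivalent. These values lie around the 0.8 mg daily dose. On single-phase decay the 8 mg arm reaches the 0.8 mg level after log2(8/0.8) × T = 4.9 to 6.3 days.

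**4. Strong CYP3A4 inhibitor after stopping.** Protocol 3.4.1 recommends waiting at least 24 h after the last dose before starting one. Protocol 1.4.1 reports that with itraconazole "the half-life of BMS-986141 increased ~3-fold". If the inhibitor starts at 24 h, 2^−(24/T + 72/(3T)) = 39 to 48% is left at 96 h. This is again single-phase and so an upper figure.

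**5. Uncounted time up to five terminal half-lives.** 7.3 − 4 = 3.3 days to 9.5 − 4 = 5.5 days per subject. As a share of the present window this is 10 to 17% of 32 days (28 + 4) in Part 1, and 3.5 to 5.8% of 94 days (90 + 4) in Part 2. The share is larger for subjects who stop early.

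**The case against.** **Late events are not lost.** SAP 7.6.1 lists every adjudicated bleed, SAP 7.6.3 summarizes serious events to 30 days after last dose, and SAP 7.6.2 summarizes deaths by arm with no post-dose limit. A reader might infer that everything after Day 4 is discarded; the documents do not support that. What stands is narrower: a listing gives no rate or interval, and the serious event summary is not an adjudicated bleeding rate.

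**The residual exposure is uncertain.** This stands. The 15 to 23% figure conflicts with the accumulation index in the same section, and on effective half-life alone little drug is left.

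**The 8 mg arm is not shown to be worst affected.** A reader might infer so from dose proportionality, but that holds only for the absolute amount. SAP 2.2 places no Phase B subjects in Part 1, so every 8 mg subject has the 90-day course, where the uncounted share is smallest. Nor do the planning assumptions help. The "relative reductions of 75% and 90% of the maximum for the 0.8 and 4.8 mg doses" in SAP 5 concern brain infarction, not bleeding, and Protocol 1.5 reports no significant bleeding in preclinical work or healthy volunteers.

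**A longer window has its own bias.** Protocol 3.4.1 bars other antithrombotics only during treatment, so Days 5 to 10 may include bleeds on therapy started after stopping, possibly at different rates across arms. This is a good reason not to replace the 4-day analysis, which already reaches beyond the endpoint's own wording. It does not count against showing both.

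**Conclusion.** The point holds as a cheap improvement. The 4-day limit is shorter than five half-lives on either protocol figure, the visible text gives no rationale, and the follow-up schedule already covers the missing days. On the joint fit about 7 to 19% of average steady-state exposure may remain at the cut-off. Across the joint and single-phase models, that is about 0.6 to 1.9 mg-equivalent in the 8 mg arm. CRNM bleeds in that interval can be missing from the primary safety rate, and minor bleeds from the all-bleeding rate.

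It is tempting to conclude that the dose-bleeding relation is biased toward no effect. That would follow only if bleeding risk tracks residual exposure over those days, and the visible text gives neither a concentration-bleeding relation nor an expected bleeding rate. The number of missed events and the size and direction of any bias cannot be computed. The exposure figures rest on mean half-lives in fasted healthy subjects.

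**What to change.** - In SAP 7.6.1 and 7.6.4 keep the 4-day analysis and state its rationale. Pre-specify, as a sensitivity analysis, the same bleeding rates, differences and CIs and the same adverse event tables through 10 days after last dose, identically in all arms. Ten days covers five of the longest stated half-life (9.5 days).
- Use one stated window for the NIHSS and lacunar breakdowns in SAP 7.6.1, and say how it relates to the endpoint definition in SAP 4.4.
- Flag bleeds that occur on antithrombotics started after the last dose. SAP 7.4.4 counts as concomitant only medication taken before the last dose, so the flag needs its own definition. The follow-up visit already records concomitant medications.
- Reconcile the half-life in Protocol 1.4.1.1 with the 6 days in Protocol 3.3.1. Which figure is right is for the sponsor to determine.

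The cost is SAP wording, one programming parameter, the flag and a second set of tables; no new data are needed. The downside is that Days 5 to 10 will add some bleeds unrelated to study drug, possibly unequally across arms, which is why the two windows should be shown side by side.
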